## Adverse Events

The participants will regularly be asked if they had experienced any uncomfortable problems or difficulties (i.e., adverse events). The participants will also be asked to notify the research staff immediately of any adverse events. Qualia Life Sciences will follow the standard guidance on reviewing and reporting on any unanticipated problems involving risk to subjects or other adverse events by assessing whether the adverse event is:

1. unexpected;
2. related or possibly related to participation in the research; and
3. serious or otherwise one that suggests that the research places subjects or others at a greater risk of physical or psychological harm than was previously known or recognized.

If Qualia Life Sciences determines that all three of the listed conditions are met, we will immediately inform the Institutional Review Board of the adverse event and related risks to research subjects or others.

---

## Intended Use Of Study Data

De-identified, aggregated outcomes from this investigation may be used by Qualia Life Sciences to support peer-reviewed publications, posters or oral presentations at scientific and medical conferences, and marketing materials. No individual-level or personally identifiable information will appear in any external communication.

---

## Appendices

### Appendix 1: Safety and Tolerability

Have you experienced any of the following while taking this product?

1. Increased anxiety/ worry
  - a. a great deal
  - b. a lot
  - c. a moderate amount
  - d. a little
  - e. not at all
2. Headache
  - a. a great deal
  - b. a lot
  - c. a moderate amount
  - d. a little
  - e. not at all
3. Mood changes (e.g., anxiety, depression, irritability)
  - a. a great deal
  - b. a lot
  - c. a moderate amount
  - d. a little
  - e. not at all
4. Stomach upset/ nausea
  - a. a great deal
  - b. a lot
  - c. a moderate amount
  - d. a little
  - e. not at all
5. Dizziness
  - a. a great deal
  - b. a lot
  - c. a moderate amount
  - d. a little
  - e. not at all
6. Bloating
  - a. a great deal
  - b. a lot
  - c. a moderate amount

- d. a little
- e. not at all

7. Itching

- a. a great deal
- b. a lot
- c. a moderate amount
- d. a little
- e. not at all

8. Sexual dysfunction

- a. a great deal
- b. a lot
- c. a moderate amount
- d. a little
- e. not at all

9. Any comments or other undesirable effects?

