## Study Schedule

Days 1-28 are when participants will take the test formulas or placebo.

Screening (prior to enrollment (Day -21 to -15): Complete online prescreen questionnaire and provide electronic informed consent.

Baseline Assessments (Day -14 to -7):

1. Conduct Ulta Labs Vitamin C Test
2. Complete PROMIS Cognitive Function - Short Form 8a
3. Complete Perceived Stress Scale-10
4. Complete Single-item Assessment of Immune Fitness
5. Complete Safety and Tolerability survey

Note: Successful completion of baseline assessments and conformation of lab draw are required to ship a participant the study product.

Day 7 Assessments: Complete Safety and Tolerability survey.

Day 14 Assessments:

1. Complete PROMIS Cognitive Function - Short Form 8a
2. Complete Perceived Stress Scale-10
3. Complete Single-item Assessment of Immune Fitness
4. Complete Safety and Tolerability survey

Day 21 Assessments: Complete Safety and Tolerability survey.

Day 29 Assessments:

1. Conduct Ulta Labs Vitamin C Test
2. Complete PROMIS Cognitive Function - Short Form 8a
3. Complete Perceived Stress Scale-10
4. Complete Single-item Assessment of Immune Fitness

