## 5. Complete Safety and Tolerability survey

Note: Participants should have blood drawn the day after their last supplement dose (ideally following an overnight fast and about 18–24 hours after their last dose of the supplement or placebo). This better reflects steady-state or trough plasma vitamin C, less influenced by the acute post-dose spike, and is the preferred approach in clinical and pharmacokinetic research to evaluate chronic supplementation effects, sustained tissue saturation, and baseline improvement. It is fine to have the participants complete the questionnaires on this same day (29) rather than day 28.

Follow-Up (Day 34-36): Complete post-study exit questionnaire.

Check-in Schedule: Day 1, 3, 7, 14, 21, 28

Note: Participants will complete regular check-in surveys to assess adherence and safety throughout the active supplementation period.

---

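### The Safety and Tolerability form lets one episode be reported under two items and at several visits, so per-visit frequencies may not separate resolved from persistent symptoms

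*Combined protocol and SAP*

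**What the plan says.** The Secondary Objectives rely on this custom survey to describe side effects. Appendix 1 gives eight graded symptom items and one open item under a single stem: "Have you experienced any of the following while taking this product". Item 1 is "Increased anxiety/ worry". Item 3 reads "Mood changes (e.g., anxiety, depression, irritability", with anxiety as its first example. The Risk And Benefits section lists increased anxiety and mood changes as two separate risks.

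The Study Schedule gives the form four times after dosing starts: "Day 7 Assessments: Complete Safety and Tolerability survey"; as the fourth entry under "Day 14 Assessments"; "Day 21 Assessments: Complete Safety and Tolerability survey"; and, in the Day 29 list, "5. Complete Safety and Tolerability survey". It is also given at "Baseline Assessments (Day -14 to -7", before product is shipped. That administration is set aside here, because the point concerns the on-treatment forms.

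Appendix 1 has no scoring section, whereas Appendices 4 to 7 each have one. Statistical Methodology offers only counts with percentages for categorical data. It does not define incidence, and it has no rule for telling a new symptom from a continuing one.

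**The concern.** Two features of the form blur what a positive answer means.

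The first is overlap. A participant with anxiety and no other mood symptom answers correctly by endorsing both items 1 and 3. The item 3 frequency then mixes anxiety with depression and irritability, although the protocol treats anxiety and mood change as distinct risks.

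The second is the open recall period. On Day 29 the stem can fairly be read as covering the whole time on product, or as covering the days since the last form. The other repeated scales settle this: PROMIS uses seven days, the PSS-10 uses one week, and the immune fitness item asks about the present moment. The safety form does not. A Day 29 percentage may therefore be cumulative incidence, current prevalence, or a blend of the two.

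At stake is the descriptive tolerability profile, a stated secondary objective. A brief early intolerance could look the same as one that lasted four weeks.

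**Working it through.** The plan states no figure on this point, so there is nothing to reproduce. The check is a count of where one episode can appear, followed by a comparison of answer patterns.

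**Inputs.** Items that anxiety fits: 2 (Appendix 1, items 1 and 3). On-treatment surveys: 4, on Days 7, 14, 21 and 29 (Study Schedule). Arm size: 18 (Number of Participants).

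**Cells per anxiety episode.** Maximum positive cells = 2 items x number of surveys on or after onset, if the participant reads the stem as cumulative:

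| Onset | Surveys left | Maximum cells |
|---|---|---|
| By Day 7 | 4 | 2 x 4 = 8 |
| Days 8-14 | 3 | 2 x 3 = 6 |
| Days 15-21 | 2 | 2 x 2 = 4 |
| After Day 21 | 1 | 2 x 1 = 2 |

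A symptom that fits one item only, such as dizziness, gives at most 1 x 4 = 4 cells.

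**What the patterns can show.** Take a symptom that starts on Day 3.

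| Course and reading of the stem | Day 7 | Day 14 | Day 21 | Day 29 |
|---|---|---|---|---|
| Resolved on Day 4, cumulative reading | yes | yes | yes | yes |
| Resolved on Day 4, recent-period reading | yes | no | no | no |
| Persistent, either reading | yes | yes | yes | yes |

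The first and third rows are identical, so duration and resolution cannot be recovered. Recurrence is hidden in the same way, because under a cumulative reading every survey after the first yes is also yes. The first positive survey still dates first onset to Days 1-7, 8-14, 15-21 or 22-29. Whether a participant ever reported the symptom is the same in all three rows.

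**Effect on a per-visit frequency.** If all 18 in an arm answer, one participant who re-endorses a resolved symptom adds 1/18 = 5.6 percentage points at that visit. Two add 2/18 = 11.1 points.

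**After rewording.** With one anxiety item and recall limited to the time since the last completed form, an episode that starts and ends within one interval appears in 1 x 1 = 1 cell. An episode that spans all four intervals still appears in 1 x 4 = 4, which is correct for by-interval reporting. That is why a per-participant summary is needed as well.

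**The case against.** A reader might infer that the survey double-counts adverse events. The documents do not support that. Nothing in them sums items, sums visits or converts survey answers into event counts. In a table by item and visit, each participant appears once per cell, and the figure of 8 is a total that the plan never calculates.

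A reader might also infer that onset is lost, or that frequencies will necessarily look flat or rising. Neither follows. First onset can be placed from the first positive survey. The flat or rising shape depends on participants reading the stem cumulatively and re-endorsing resolved symptoms, and the documents do not say how they will read it. The usual summary, participants with at least one endorsement, can already be derived from the present form.

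Nor is item 3 always ambiguous. If it is positive and item 1 is answered at the lowest grade, anxiety is largely excluded. Item 9 also takes free text.

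Other safety data exist. Check-ins on Days 1, 3, 7, 14, 21 and 28 include a side-effect question, and participants are told to report adverse events at once. This is partial relief only, because the check-in question has no recall window, symptom list, or start and stop dates.

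Finally, both arms of a blinded trial complete the same form, so the blurring is not differential by design. An open stem also has one merit: symptoms from a missed survey can still be captured at the next one. All of this stands and limits the point. It does not remove the mixed item 3 or the loss of resolution, and the recall problem affects a single-visit table without any summing.

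**Conclusion.** The point holds in a limited form. Item 3 is mixed whenever items 1 and 3 are both endorsed. The open stem means that per-visit frequencies may not separate resolved from persistent symptoms, so duration, resolution and recurrence are lost. First onset and ever-reported incidence are kept.

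The size is at most 8 item-by-visit cells for one early anxiety episode, and 5.6 percentage points on a visit's frequency per re-endorsing participant. Both figures assume a cumulative reading of the stem, and the second also assumes that all 18 in the arm respond. The 5.6 points is an absolute figure for one arm at one visit and is not an estimate of between-arm bias. The effect is confined to descriptive safety data, and the primary vitamin C comparison is unaffected. This is a minor improvement, worth making because information on resolution cannot be recovered from these answers afterwards.

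**What to change.** 1. Reword item 3 as *Mood changes other than anxiety (e.g., depression, irritability)*.
2. On the Day 7, 14, 21 and 29 forms, ask about the time *since you last completed this survey*. On the first on-treatment form a participant completes, ask *since you started the product*. Anchoring to the last completed form is preferable to a fixed seven days: the Study Schedule gives no completion windows for the Day 7, 14 and 21 surveys, and a fixed period would leave gaps or overlap when a form is late or missed.
3. State in Statistical Methodology that each symptom will be reported by survey interval and as the number and percentage of participants with at least one on-treatment endorsement, one count per participant per symptom.

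The cost is a wording change to an electronic form, with a different stem on the first form completed, and a sentence in the analysis section. No items or visits are added. The small downside is unequal intervals when a survey is late or missed. Even on schedule, the last interval (Days 22-29) is eight days against seven for the others.

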### Secondary Objectives

To assess within-group and between-group differences in PROMIS Cognitive Function - Short Form 8a, Perceived Stress Scale-10 domain scores, and Single-item Assessment of Immune Fitness.

To assess within-group differences in the change in blood Vitamin C levels.

To evaluate side effect profiles using a custom Safety and Tolerability survey.

---

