## Risk And Benefits

The potential risks and benefits of participating in this study will be fully explained to participants in their informed consent documentation. Risks include potential side effects from the product—nausea, diarrhea, bloating, headache, dizziness, increased anxiety, mood changes, itching, sexual dysfunction, and the possibility of drug-drug interactions—as well as the possibility of no improvement in blood Vitamin C levels or symptoms assessed by PROMIS Cognitive Function - Short Form 8a, the Perceived Stress Scale-10 measures, and Single-item

Assessment of Immune Fitness. Benefits include the potential for increased blood vitamin C levels, decreased oxidative stress, supporting the body's natural immune responses, and improvement in quality of life.

No adverse effects in human trial studies have been reported in the reviewed literature regarding the ingredients in the active product at the doses used in this study. It is extremely unlikely that participants will experience health complications due to dosage amount. If any adverse events occur, [name], ND, will assess the appropriate treatment and action (e.g., seek medical treatment). Qualia Life Sciences is not able to offer financial compensation should a participant be injured as a result of participating in this research. However, participants are not precluded from seeking to collect compensation for injury related to malpractice, fault, or blame on the part of those involved in the research. This information is included in the consent form.

---

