## Appendix 2: Check-in

1. How many days this week (past 7 days) did you take the product?
2. How many capsules did you usually take each day?
3. What time during the day did you usually take the product?
4. Did you usually take the product with an empty or full stomach?
5. Have you noticed any side effects from taking the product?
6. Is there anything you would like to say?

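### Diarrhea is the only one of nine named symptom risks without a graded item in the safety survey, so it is likely to be under-reported relative to the others and cannot be tabulated with them

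*Combined protocol and SAP*

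**What the plan says.** Under Secondary Objectives, the protocol states one aim as "To evaluate side effect profiles using a custom Safety and Tolerability survey". That survey is Appendix 1. The Study Schedule gives it at baseline and on Days 7, 14, 21 and 29.

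The Risk And Benefits section lists the symptoms that the product might cause: "nausea, diarrhea, bloating, headache, dizziness, increased anxiety, mood changes, itching, sexual dysfunction". It adds possible drug-drug interactions, which are not a symptom.

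Appendix 1 has eight items answered on a five-level scale, then a ninth, open item: "Any comments or other undesirable effects". The graded items closest to diarrhea are item 4, "Stomach upset/ nausea", and item 6, on bloating.

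Two other routes exist outside the survey. Question 5 of the check-in (Appendix 2) asks "Have you noticed any side effects from taking the product", and check-ins fall on Days 1, 3, 7, 14, 21 and 28. The Adverse Events section also provides for regular general questioning about problems and asks participants to tell staff at once if one occurs.

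**The concern.** The graded items follow the risk list closely, with one gap, and the documents give no reason for it. Eight symptoms are prompted by name and rated for severity at each of five administrations. Diarrhea depends on the participant raising it unprompted, or on its being folded into a broader item.

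Symptoms collected in these two ways are not comparable. A prompted symptom has a rating from everyone who completes the survey, including an explicit answer that it did not occur. For an unprompted symptom, silence may mean that it was absent or merely that it was not mentioned. In a tolerability table, diarrhea would either have no row or have a row with a different meaning from the rest. The section on Intended Use Of Study Data allows aggregated results to go into publications and marketing materials, so the table may be read without knowledge of how each symptom was collected.

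**Working it through.** **Step 1: match the two lists.** The left column is from Risk And Benefits and the right from Appendix 1.

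| Named symptom risk | Graded item |
|---|---|
| Nausea | 4 (with stomach upset) |
| Diarrhea | none |
| Bloating | 6 |
| Headache | 2 |
| Dizziness | 5 |
| Increased anxiety | 1 (also an example in item 3) |
| Mood changes | 3 |
| Itching | 7 |
| Sexual dysfunction | 8 |

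Coverage is 8 of 9. Items 1 to 9 run in unbroken sequence, so the gap is not a loss in the text.

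**Step 2: what the remaining routes record.**

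- Item 9 of the survey: free text, no grade, no symptom named.
- Check-in question 5: general, no grade, and it asks about effects of the product, so the participant must first attribute the symptom to it.
- Adverse event inquiry: general, with no symptom list and no severity scale described.
- Item 4 of the survey: graded, but a rating there cannot be separated into nausea, stomach upset or diarrhea.

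**Step 3: illustrate the effect of incomplete capture.** The plan gives no figure to reproduce. The one input from the documents is n = 18 per arm (Number Of Participants). The incidence p and the share c of cases that come to light are assumptions. If participants are independent, the chance of recording at least one case on active is

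P = 1 − (1 − p·c)^18.

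With p = 10%:

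| c | p·c | P |
|---|---|---|
| 100% | 0.10 | 1 − 0.90^18 = 0.850 |
| 70% | 0.07 | 1 − 0.93^18 = 0.729 |
| 50% | 0.05 | 1 − 0.95^18 = 0.603 |
| 30% | 0.03 | 1 − 0.97^18 = 0.422 |

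With p = 20%, the results are 1 − 0.80^18 = 0.982 at full capture and 1 − 0.94^18 = 0.672 at c = 30%. The row for 100% is an upper limit, because a graded item need not capture every case either.

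**Step 4: baseline wording.** The Appendix 1 stem asks about symptoms during use of the product. The Study Schedule ships product only after the baseline assessments are complete. An item added under the present stem would therefore have no meaningful baseline answer, and the same applies to the eight existing items.

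**The case against.** The strongest reply is that diarrhea has many chances to be reported. Item 9 is put to participants on four occasions after dosing starts (Days 7, 14, 21 and 29) and check-in question 5 on six, which makes ten open prompts, besides the adverse event inquiry. A participant with diarrhea might also reasonably grade it as stomach upset. This stands as an answer to any claim that diarrhea would go unrecorded. It does not supply a severity rating specific to diarrhea or put the symptom on the same footing as the other eight.

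A second reply is that both arms use the same blinded instruments, so incomplete reporting should affect both. This also stands: nothing in the documents shows a bias towards either arm. The likely effect is fewer recorded cases and a smaller absolute difference.

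A third is that a graded item would add little inferential strength at this size. With 2 of 18 against 0 of 18, the one-sided Fisher probability is C(18,2)/C(36,2) = 153/630 = 0.243, and the two-sided p is 0.486. The Statistical Methodology section names no severity test for the survey items. The loss is therefore to description, which is what a side-effect profile mainly consists of.

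A reader might go further and infer that the survey will report diarrhea as rare or absent and so give a falsely favourable gastrointestinal profile. The documents do not support that. The open routes may catch cases, item 4 may absorb some, and no rate of unprompted capture is given.

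**Conclusion.** The gap in the instrument is certain: diarrhea alone among the nine named symptom risks has no prompted severity rating at any administration. Under-reporting relative to the other eight is likely but not established, and its size cannot be computed from the documents. The figures of 85% falling to 73%, 60% or 42% rest on an assumed 10% incidence, assumed capture rates, independence between participants and full capture as the comparator. They show how sensitive a sample of 18 is to missed cases and do not predict this trial's result.

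The point concerns one symptom within one secondary objective. The primary outcome, the sample size and the main analysis are unaffected. It is still worth correcting, because prompted ratings that were never collected cannot be recovered afterwards.

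**What to change.** Add a graded item, *Diarrhea / loose stools*, to Appendix 1 on the same five-level scale, at every scheduled administration (baseline and Days 7, 14, 21 and 29). Give the baseline version a stem that does not refer to taking the product, for example *in the past 7 days*, and apply it to all graded items so that baseline answers can be interpreted. Tabulate the new item by arm and severity with the other eight. Keep the open item, the check-in question and the adverse event inquiry as they are.

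The cost is one extra line in an electronic survey, the change of baseline stem and the related IRB submission. No design figure changes, and graded coverage of the named symptom risks goes from 8 of 9 to 9 of 9.

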## Appendix 2: Check-in

1. How many days this week (past 7 days) did you take the product?
2. How many capsules did you usually take each day?
3. What time during the day did you usually take the product?
4. Did you usually take the product with an empty or full stomach?
5. Have you noticed any side effects from taking the product?
6. Is there anything you would like to say?

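### Check-in item 5, and in part survey item 9, ask for effects of the product, whereas the Adverse Events section promises a neutral question; unlisted events the participant does not blame on the product go unsolicited

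*Combined protocol and SAP*

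**What the plan says.** The Adverse Events section makes two commitments.

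- **Asking.** "The participants will regularly be asked if they had experienced any uncomfortable problems or difficulties (i.e., adverse events". Nothing in that sentence restricts the question to problems the participant links to the product.
- **Judging.** The sponsor assesses three criteria, one of which is whether the event is "related or possibly related to participation in the research". The other two concern unexpectedness and seriousness or increased risk. If the sponsor finds all three met, it informs the IRB immediately.

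The same section separately tells participants to notify staff at once of any adverse event.

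The forms that carry out the asking are in the appendices. The Study Schedule says of the check-in: "Participants will complete regular check-in surveys to assess adherence and safety throughout the active supplementation period". It gives the timing as "Check-in Schedule: Day 1, 3, 7, 14, 21, 28". The form itself (Appendix 2) has one safety question, item 5: "Have you noticed any side effects from taking the product". Item 6 is open: "Is there anything you would like to say".

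The Safety and Tolerability survey (Appendix 1) grades eight symptoms under a stem that refers to the period of taking the product. It ends with item 9: "Any comments or other undesirable effects". After baseline it is scheduled on Days 7, 14, 21 and 29.

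**The concern.** An adverse event question should collect the event first and settle causality afterwards. The Adverse Events section follows that order, but check-in item 5 reverses it. A participant who has a health problem and blames a meal, a virus or a bad night can truthfully answer no. Survey item 9 shares the problem in part, because its safety wording speaks of effects.

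Two things are at stake. First, an event that is never solicited may not reach the sponsor's review of relatedness and seriousness, and so may not be tested against the IRB reporting rule. Second, answers to item 5 can depend on which product participants think they received, because someone who believes they are on placebo has less reason to call a symptom a side effect. The Summary says assessments, including questionnaires, are completed remotely, and the Study Schedule lists no clinical interview. The wording of the forms therefore largely determines what is solicited.

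**Working it through.** No plan figure is in dispute and no power or error-rate calculation applies. The check compares the texts and counts the schedule.

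**Step 1. Each route by which an event can reach the sponsor.**

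| Route | When | Must the participant attribute it to the product? | Prompts for unlisted health events? |
|---|---|---|---|
| Regular question promised in Adverse Events | No day or form named | No | Yes |
| Check-in item 5 | Days 1, 3, 7, 14, 21, 28 | Yes | Only if attributed |
| Check-in item 6 | Same days | No | No; open text, not framed as safety |
| Survey items 1 to 8 | Days 7, 14, 21, 29 | No; wording is temporal | No; eight fixed symptoms |
| Survey item 9 | Same days | In part: it invites comments, but its safety wording is about effects | In part |
| Participant notifies staff | Any time | No | Not a prompt |

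The neutral question in the first row appears on none of the forms shown.

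**Step 2. Scheduled contacts.** Check-ins: 6 (Days 1, 3, 7, 14, 21, 28). Post-baseline surveys: 4 (Days 7, 14, 21, 29). Total forms: 6 + 4 = 10. Both fall on Days 7, 14 and 21, so the distinct days number 10 − 3 = 7. The check-in is the only scheduled safety form on 3 of them: Days 1, 3 and 28.

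**Step 3. What those three days lose.** The survey stem sets no recall limit. A listed symptom on Day 1 or 3 can be reported on the Day 7 survey, and one on Day 28 on the Day 29 survey. The loss on these days is therefore confined to unlisted events.

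**Step 4. Does any foreseeable event fall outside the list?** Risk And Benefits names nine symptoms: nausea, diarrhea, bloating, headache, dizziness, increased anxiety, mood changes, itching and sexual dysfunction. Appendix 1 has an item for every one except diarrhea, so 9 − 8 = 1 risk named by the plan has no item of its own. A participant with diarrhea who blames food can answer no to item 5 and enter nothing under item 9. Some might tick the stomach upset and nausea item, but the record would not show diarrhea. Infections and injuries are likewise unlisted.

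**The case against.** The strongest reply is that safety collection does not rest on item 5. The Secondary Objectives name the Safety and Tolerability survey, not the check-in, as the tool for side effect profiles, and its eight symptoms need no attribution. Check-in item 6 gives an open route at all six check-ins, and survey item 9 invites any comments. Participants are told to report any adverse event immediately, with no attribution condition. Appendix 4 also asks, without attribution, whether the participant became sick after contact with a contagious person. Finally, Outcome Measures lists a Follow-Up Questionnaire that no appendix reproduces under that title, so its content cannot be checked.

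Most of this stands, and it rules out several stronger readings that a reader might infer:

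- *Participants decide causality for the trial's safety data as a whole.* Not so for the eight listed symptoms.
- *Unattributed events never reach the sponsor.* Spontaneous reporting and free text remain open.
- *Every event on Days 1, 3 and 28 is affected.* Step 3 shows that listed symptoms can be recovered at the next survey.
- *A given fraction, such as half, of related events is lost.* The documents contain nothing from which a fraction could be estimated.
- *Arm comparisons of side effects are contaminated by guesses about allocation.* This does not follow for the eight symptoms from item 5's wording, and the plan states no between-arm analysis of item 5.

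The reply does not remove the mismatch. Spontaneous notification is a separate commitment from regular asking, and an open comment box that does not mention health is a weak substitute for a direct question. The Appendix 4 item covers one kind of illness, once, after dosing has ended.

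**Conclusion.** The concern holds in a narrow form. Check-in item 5, and survey item 9 in part, ask the participant to make a judgement that the Adverse Events section gives to the sponsor, and no form shown asks the neutral question that section promises. The consequence is limited to solicited capture of events outside the eight listed symptoms that the participant does not attribute to the product. Such events may miss the relatedness, seriousness and IRB review. If item 5 answers were ever tabulated by arm, they could also partly reflect guesses about allocation.

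Its size cannot be put as a rate. The primary outcome, the sample size and the eight-symptom profile are untouched.

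The conclusion assumes that the Follow-Up Questionnaire does not contain the neutral question, and that no unscheduled contact delivers it. If either does, the gap is smaller, but the inconsistency between the forms and the Adverse Events section remains.

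**What to change.** Reword check-in item 5 and survey item 9 so that both match the Adverse Events section. Suggested text: *Since you last completed one of these forms (or since your first dose, if this is the first), have you had any new or worsened symptom, illness, injury or medical visit, whether or not you think it is related to the product? If yes, please describe it, say when it started, and say whether it has stopped or is continuing.* Anchoring to the last completed form means a missed form leaves no uncovered period.

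If the participant's own view of cause is wanted, ask it as a separate, optional item after the event has been recorded. Leave relatedness to the sponsor's assessment, as the plan already states. It would also help for the Adverse Events section to name the forms through which participants are regularly asked.

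The change is to the wording of two items on electronic forms. The downside is a few more trivial events to review among about 36 participants.
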